8.10.1.1 Adverse Events to Monitor

Adverse events to be monitored are included in Appendix 10.7 by MedDRA preferred terms in categories of gastrointestinal AEs and liver-related investigations.

Tables summarizing patient incidents for the monitored adverse events will be generated.

8.10.2 Laboratory Parameters

Clinical laboratory data will be summarized descriptively by the type of laboratory test and by time point. The frequency and percentage of subjects who experience abnormal clinical laboratory results (i.e. outside of reference ranges) and/or clinically significant abnormalities will be reported by shift tables. For each clinical laboratory measurement, descriptive statistics will be provided for study baseline and all subsequent post-treatment scheduled visits. Changes from study baseline to the post-treatment visits will also be provided.

8.10.3 Prior and Concomitant Medications

Prior medication is defined as any medication started before the date of the first dose of investigational product. Concomitant medication is defined as any medication taken on or after the date of the first dose of investigational product. Any concomitant medications started after the date of the last dose of investigational product will not be presented in the summary tables but will be included in the subject data listings.

Each medication will be coded to a preferred name and an Anatomic Therapeutic Classification (ATC) code using WHODrug. The number and percentage of subjects taking each concomitant medication will be displayed by preferred name. If a subject took a specific medication multiple times or took multiple medications within a specific therapeutic class, that subject will be counted only once for the coded drug name or therapeutic class. Prior and concomitant medications will be listed.

8.10.4 Physical Examinations

Physical examinations will be performed at baseline, week 12, week 24, week 36, and week 48 or termination visit. At baseline and week 48, a full physical examination will be conducted including a neurological examination. A brief physical examination will be conducted at other visits. The full examination assesses the general appearance, HEENT, cardiovascular, dermatologic, lymphatic, respiratory, gastrointestinal, and musculoskeletal; the brief physical examination assesses the general appearance, cardiovascular, and respiratory; the neurological examination assesses the cognition, cranial nerves, motor

function, coordination and gait, reflexes, and sensory function. Full physical and neurological examinations will be summarized using shift tables. Results from brief physical examinations will be listed.

8.10.5 Vital Signs

Vital signs will include seated systolic blood pressure and diastolic blood pressure measured in millimeters of mercury (mmHg), heart rate in beats per minute, respiration rate in breaths per minute, and temperature in degrees Celsius (°C). Vital signs measurements will be performed at every visit and will be reported in a listing.

8.10.6 Interval History

Each interval history is intended to record any signs, symptoms, or events (i.e., falls) experienced by the subject since the prior study visit that are not related to study procedure(s) performed at prior study visits or study drug. Interval history may identify under-reported AEs. Interval history for all subjects will be reported in a listing.

8.10.7 Suicidal ideation and behavior

The Columbia Suicide Severity Rating Scale (C-SSRS) is a standardized rating instrument used to assess the suicidal ideation and behavior in an at-risk population (Posner et al. 2011) and will be administered at each visit. The C-SSRS will be listed.

8.10.8 Urine Testing for ManNAc

ManNAc will be assessed at each visit to detect noncompliance with prohibited medication restrictions. The ManNAc results for all subjects in the Safety Analysis Set will be reported in listing format.

8.10.9 Pregnancy Test

Pregnancy test will be conducted at each study visit and the results will be provided in a listing.

10 APPENDICES

10.1 Efficacy Endpoints Definition Details

10.1.1 GNEM Functional Activities Scale Expanded Version

The GNEM-FAS (also referred to as HIBM-FAS in some studies) expanded version is a disease-specific measure developed to assess the functional impact of changes in muscle strength. The scale consists of 3 domains: upper extremity, mobility, and self-care; scores for each domain and a total score will be obtained. The GNEM-FAS expanded version will be administered at each visit beginning with the Screening Visit to evaluate physical functioning. Test administration at the Screening visit is intended to provide experience and familiarize the subject with the assessments for the evaluator and the subject, and data collected will not be used for analysis. The scale has been developed specifically for patients with GNEM based on feedback received from affected individuals on the impact of the disease on their function. Items in the scale assess the subject's ability to independently perform various activities of living that involve self-care, mobility and use of the upper and lower extremities. The original GNEM-FAS was developed as a clinician-reported outcome measure (ClinRo) for ambulatory GNEM patients but has since been modified to include additional items to accommodate weaker patients. This modified version is referred to as the GNEM-FAS Expanded Version and will be used in this study.

GNEM Functional Activities Scale (GNEM-FAS) Expanded Version Total Score will be calculated as the sum of the Total Scores range from 0 to 120 with higher scores representing greater independence with functional activities. Subscale scores will be calculated for the Mobility, Upper Extremity and Self-Care domains. Mobility subscale scores have 13 items and range from 0 to 52 with higher scores representing greater mobility. Upper Extremity subscale scores have 9 items and range from 0 to 36 with higher scores representing more skilled, independent use of the arms during functional activity performance. Self-Care subscale scores have 8 items range from 0 to 32 with higher scores representing greater independence with functional care activities. The maximum possible for the total score is 120.

10.1.2 Short Form – 36 Item (SF-36)

The SF 36 will be completed by subjects at each visit beginning with the Baseline Visit to assess physical and mental health based on 8 scaled scores that are the weighted sums of the questions in their section: vitality, physical functioning, bodily pain, general health perceptions, physical role functioning, emotional role functioning, social role functioning, and mental health. Each scale is directly transformed into a 0 to 100 scale on the assumption that each question carries equal weight. Lower scores indicate more diminished health-related quality of life.

The scale and component scores will be calculated according to the standard scoring algorithm published along with the SF-36 (Ware et.al. 1995 and Ware et.al. 2007). The z

scores of domain scales will be aggregated to generate the component scores PCS and MCS using weights derived from the U.S. general population. The component scores will be scaled to have a mean of 50 and standard deviation of 10 using a linear transformation. The component scores will not be calculated unless all relevant domain scale scores are available. Details of the scoring algorithm can be found in Appendix [10.4](#).

10.2 Predicted HHD Normal Muscle Strength

Muscle strength of interest for this study includes grip, key pinch, shoulder abductors, wrist extensors, and knee extension.

Note: Many of the HHD derived variables detailed below rely on regression equations that have predictor variables in units different than what is found in the analysis datasets. Care will be taken to convert dataset variables to the correct units before they are entered into the prediction equation. The resulting predicted value will then, in turn, be converted to the appropriate unit for analysis.

Shoulder abduction and hip abduction

Regression Equations and Multiple Correlations of Sex, Age, and Weight with Muscle Strength

Muscle Action	Side	Equation*	R	R ²
Shoulder Abduction	Nondominant	$165.16 - 74.9S - .910A + .126W$.843	.710
	Dominant	$178.90 - 77.1S - 1.128A + .134W$.843	.710

(Bohannon 1997)

*Muscle strength results in Newtons (N). S, sex (male=0, female=1); A, age (years); W, weight (Newtons).

Note: Age and weight values collected at the Baseline visit will be used for the calculation of predicted values for shoulder abduction for all study time points.

Gross Grip

Normative grip strength values for the Jamar dynamometer for clinical use (in pounds)

Age (years)	Females (n = 355)			Males (n = 365)		
	Number of subjects	5 th %ile Jamar values (lbs)	Median Jamar values (lbs)	Number of subjects	5 th %ile Jamar values (lbs)	Median Jamar values (lbs)
20 - 29	51	50	62	50	81	100
30 - 39	50	49	64	51	80	105
40 - 49	50	48	63	50	78	107
50 - 59	51	45	61	54	73	104
60 - 69	49	40	56	58	64	95
70 - 79	50	32	46	50	51	77
≥ 80	54	22	34	52	34	54

(Peters et al. 2011)

Note: The age category that applies for a subject at the Baseline visit will be used for the calculation of predicted grip values for all study time points.

Table 6: Regression Equations and Multiple Correlations of Sex, Age, and Weight with Muscle Strength (Newtons)

Muscle Action	Side	Equation*	R	R ²
Wrist extension	Non	114.36 - 45.1S - .774A + .094W	.825	.680
	Dom	123.65 - 48.5S - .784A + .092W	.826	.683
Elbow flexion	Non	188.25 - 89.2S - .650A + .132W	.882	.779
	Dom	188.36 - 96.5S - .610A + .140W	.907	.822
Elbow extension	Non	150.37 - 71.5S - 1.044A + .126W	.852	.726
	Dom	156.49 - 73.0S - 1.032A + .116W	.853	.727
Shoulder lateral rotation	Non	140.32 - 50.2S - 50.164A + .080W	.786	.618
	Dom	147.66 - 54.5S - .930A + .088W	.810	.656
Shoulder extension	Non	260.18 - 113.5S - 1.868A + .202W	.842	.709
	Dom	278.99 - 120.0S - 1.99A + .202W	.855	.731
Shoulder abduction	Non	165.16 - 74.9S - .910A + .126W	.843	.710
	Dom	178.90 - 77.1S - 1.128A + .134W	.843	.710
Ankle dorsiflexion	Non	302.54 - 60.9S - 2.203A + .159W	.742	.550
	Dom	285.46 - 47.6S - 2.367A + .193W	.669	.448
Knee extension [†]	Non	480.70 - 95.0S - 4.868A + .310W	.826	.683
	Dom	465.22 - 84.7S - 4.803A + .325W	.820	.673
Hip flexion	Non	216.48 - 74.6S - .926A + .026W	.718	.516
	Dom	219.30 - 72.6S - .977A + .027W	.731	.534
Hip abduction	Non	203.32 - 73.3S - 1.247A + .192W	.794	.630
	Dom	195.24 - 62.4S - 1.184A + .198W	.764	.584

*S, sex (male = 0, female = 1); A, age (years); W, weight (Newtons).

[†]The equations for knee extension are compromised by the upper limit of force (650N) recorded for 21 subjects.

Wrist extension ([Bohannon 1997](#))

Pinch Strength Norms for Adults

Average Performance of All Subjects on Key Pinch (kg.)

		Men			Women		
Age	Hand	Mean	SD	Range	Mean	SD	Range
20-24	R	11.8	1.6	9.5-15.4	8.0	0.9	6.4-10.4
	L	11.2	1.5	8.6-14.1	7.3	1.0	5.9-10.4
25-29	R	12.1	2.2	8.6-18.6	8.0	1.0	6.4-10.0
	L	11.3	2.0	8.6-17.7	7.5	1.0	5.9-10.0
30-34	R	12.0	2.2	9.1-16.3	8.5	1.4	5.9-11.3
	L	11.9	2.3	7.7-16.3	8.1	1.6	5.4-11.8
35-39	R	11.8	1.5	9.5-14.5	7.5	0.9	5.4-9.5
	L	11.6	1.8	8.2-14.5	7.3	1.2	5.4-10.0
40-44	R	11.6	1.2	9.5-14.1	7.6	1.4	4.5-10.9
	L	11.4	1.8	8.6-14.1	7.2	1.4	3.6-10.0
45-49	R	11.7	1.8	8.6-15.9	8.0	1.5	5.9-10.9
	L	11.2	2.0	8.2-19.1	7.5	1.3	5.4-10.9
50-54	R	12.1	2.0	9.1-15.4	7.6	1.1	5.4-10.0
	L	11.8	1.9	9.1-16.8	7.3	1.2	5.4-10.0
55-59	R	11.0	1.9	8.2-15.4	7.1	1.1	5.0-9.5
	L	10.4	2.1	5.9-14.1	6.7	1.0	5.4-8.6
60-64	R	10.5	2.4	6.4-16.8	7.0	1.2	4.5-9.1
	L	10.1	1.9	7.3-15.0	6.4	1.1	4.5-8.6
65-69	R	10.6	1.8	7.7-14.5	6.8	1.2	4.5-9.5
	L	10.0	1.6	7.7-12.7	6.5	1.3	4.5-9.1
70-74	R	8.8	1.1	7.3-11.3	6.6	1.3	3.6-10.0
	L	8.7	1.4	5.9-12.7	6.3	1.4	4.1-10.0
75 +	R	9.3	2.1	4.1-14.1	5.7	1.0	3.6-7.7
	L	8.7	1.4	5.9-10.9	5.2	1.2	3.2-7.3

The above information is taken from ***Grip & Pinch Strength: Normative Data for Adults***, Arch Phys Med Rehabil 66:69-72, 1985, V. Mathiowetz, et al

10.3 Missing Observation in Hand Held Dynamometry

Missing observations in HHD will be imputed based on reason for missing and if the muscle strength measurement is missing on both sides or one side. The table below provides a summary of the imputation rule followed by detailed descriptions.

Instrument	Missing Reason	Imputation
HHD missing BOTH sides	Too Weak	0
	Too Strong	NA , UE/LE composite not computed
	Pain	NA , UE/LE composite not computed
	Injury	NA , UE/LE composite not computed
	Contracture	NA , UE/LE composite not computed
	Other	NA , UE/LE composite not computed
HHD missing ONE side	Too Weak	0
	All other reasons	The value from the other side that was measured

Missing Reason = Weakness

A value of 0 should be imputed for a W.

- If both sides are W, a value of 0 is assigned to each side and the muscle group IS counted as part of the UE or LE composite.
- If one side is W, a value of 0 is assigned to that side and the 0 is averaged with the value from the other side. The muscle group IS counted as part of the UE or LE composite.

Missing Reason = Contracture

A value of 0 should NOT be imputed for a C. A C is missing data because the test was not performed due to a joint contracture.

- If both sides are C (which would be rare), then the data for this muscle group is missing and the UE or LE composite will be set to missing.
- If one side is C, then the data is missing from this side and the value from the other side should be used to reflect the strength for this muscle group. The muscle group IS counted as part of the UE or LE composite.

Missing Reason = Pain

A value of 0 should NOT be imputed for a P. A P is missing data because the test was not performed due to pain.

- If both sides are P, then the data for this muscle group is missing and the UE or LE composite will be set to missing.
- If one side is P, then the data is missing from this side and the value from the other side should be used to reflect the strength for this muscle group. The muscle group IS counted as part of the UE or LE composite.

Missing Reason = Injury

A value of 0 should NOT be imputed for an I. An I is missing data because the test was not performed due to injury.

- If both sides are I, then the data for this muscle group is missing and the UE or LE composite will be set to missing.
- If one side is I, then the data is missing from this side and the value from the other side should be used to reflect the strength for this muscle group. The muscle group IS counted as part of the UE or LE composite.

Missing Reason = Too Strong

An S indicates that the test was attempted but that the subject overpowered the evaluator and a valid value could not be obtained.

- If both sides are S, then the data for this muscle group is missing and the UE or LE composite will be set to missing.
- If one side is S, then the data is missing from this side and the value from the other side should be used to reflect the strength for this muscle group. The muscle group IS counted as part of the UE or LE composite.

Missing Reason = OTHER

No value should be imputed if there is an O.

- If both sides are O, then the data for this muscle group is missing and the UE or LE composite will be set to missing.
- If one side is O, then the data is missing from this side and the value from the other side should be used to reflect the strength for this muscle group. The muscle group IS counted as part of the UE or LE composite.

10.4 SF-36 v2® Scoring Algorithm

Prior to any summary scores being calculated, ten items in the questionnaire will be re-coded according to the developer's instructions as follows:

	Response Choices	Pre-coded Item Value		Final Item Value
Item 1	Excellent	1		5.0
	Very Good	2		4.4
	Good	3		3.4
	Fair	4		2.0
	Poor	5		1.0
Item 6	Not At All	1		5
	Slightly	2		4
	Moderately	3		3
	Quite A Bit	4		2
	Extremely	5		1
Item 7	None	1		6.0
	Very Mild	2		5.4
	Mild	3		4.2
	Moderate	4		3.1
	Severe	5		2.2
Item 8	If both item 7 and item 8 are answered	Item 8 pre-coded value	Item 7 pre-coded value	
	Not At All	1	1	6
	Not At All	1	2 through 6	5
	A Little Bit	2	2 through 6	4
	Moderately	3	2 through 6	3
	Quite A Bit	4	2 through 6	2
	Extremely	5	2 through 6	1

	Response Choices	Pre-coded Item Value	Final Item Value
Item 8	If Item 7 is not answered		
	Not At All	1	6.0
	A Little Bit	2	4.75
	Moderately	3	3.5
	Quite A Bit	4	2.25
	Extremely	5	1.0
Item 9a, 9d, 9e and 9h	All Of The Time	1	6
	Most Of The Time	2	5
	A Good Bit Of The Time	3	4
	Some Of The Time	4	3
	A Little Of The Time	5	2
	None Of The Time	6	1
Item 11b and 11d	Definitely True	1	5
	Mostly True	2	4
	Don't Know	3	3
	Mostly False	4	2
	Definitely False	5	1

Upon appropriate re-coding of individual items, the raw scale score will be calculated as the average score over non-missing items in that scale and scaled between 0 and 100, with higher score representing better health status. The raw scale score will not be calculated unless $\geq 50\%$ of relevant questions are answered in a scale domain.

The raw scale scores will be computed by taking the sum of the items for that particular scale. Each raw scale score will then be transformed to a 0 to 100 scale using the following formula:

$$\text{Transformed Scale} = \frac{[\text{Actual raw score} - \text{Lowest possible raw score}]}{\text{Possible raw score range}} \times 100$$

This information is summarized in the following table.

Formulae for Scoring and Transforming Scales			
Scale	Sum Final Item Values	Lowest And Highest Possible Raw Scores	Possible Raw Score Range
Physical Functioning (PF)	$3a + 3b + 3c + 3d + 3e + 3f + 3g + 3h + 3I + 3j$	10, 30	20
Role-Physical (RP)	$4a + 4b + 4c + 4d$	4, 8	4
Bodily Pain (BP)	$7 + 8$	2, 12	10
General Health (GH)	$1 + 11a + 11b + 11c + 11d$	5, 25	20
Vitality (VT)	$9a + 9e + 9g + 9i$	4, 24	20
Social Functioning (SF)	$6 + 10$	2, 10	8
Role-Emotional (RE)	$5a + 5b + 5c$	3, 6	3
Mental Health (MH)	$9b + 9c + 9d + 9f + 9h$	5, 30	25

A norm-based z score for each scale will then be computed using the U.S. general population data for each scale score.

$$\begin{aligned}
 PF_Z &= (PF - 84.52404) / 22.89490 \\
 RP_Z &= (RP - 81.19907) / 33.79729 \\
 BP_Z &= (BP - 75.49196) / 23.55879 \\
 GH_Z &= (GH - 72.21316) / 20.16964 \\
 VT_Z &= (VT - 61.05453) / 20.86942 \\
 SF_Z &= (SF - 83.59753) / 22.37642 \\
 RE_Z &= (RE - 81.29467) / 33.02717 \\
 MH_Z &= (MH - 74.84212) / 18.01189
 \end{aligned}$$

The z-scores for the raw scales will be combined to form the two raw summary scores by multiplying each one by its corresponding scoring coefficient from the general U.S. population and taking the sum of those values.

$$\begin{aligned}
 AGG_PHYS &= (PF_Z * .42402) + (RP_Z * .35119) + (BP_Z * .31754) \\
 &+ (GH_Z * .24954) + (VT_Z * .02877) + (SF_Z * -.00753) + (RE_Z \\
 &* -.19206) + (MH_Z * -.22069)
 \end{aligned}$$

$$\begin{aligned}
 AGG_MENT &= (PF_Z * -.22999) + (RP_Z * -.12329) + \\
 &(BP_Z * -.09731) + (GH_Z * -.01571) + (VT_Z * .23534) + (SF_Z * \\
 &.26876) + (RE_Z * .43407) + (MH_Z * .48581)
 \end{aligned}$$

The general U.S. population means, standard deviations, and scoring coefficients are summarized in the following table:

SF-36 Scale	Mean	SD	Factor Score Coefficients	
			PCS	MCS
PF	84.52404	22.89490	0.42402	-0.22999
RP	81.19907	33.79729	0.35119	-0.12329
BP	75.49196	23.55879	0.31754	-0.09731
GH	72.21316	20.16964	0.24954	-0.01571
VT	61.05453	20.86942	0.02877	0.23534
SF	83.59753	22.37642	-0.00753	0.26876
RE	81.29467	33.02717	-0.19206	0.43407
MH	74.84212	18.01189	-0.22069	0.48581

Finally, the PCS and MCS will be standardized as follows:

$$\text{PCS} = (\text{AGG_PHYS} \times 10) + 50$$

$$\text{MCS} = (\text{AGG_MENT} \times 10) + 50$$

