#### **7.5.3.3 Medical Outcomes Survey – 36 Item (SF-36)**

The SF-36 will be completed by subjects at each visit beginning with the Baseline Visit to assess physical and mental health based on 8 scaled scores that are the weighted sums of the questions in their section: vitality, physical functioning, bodily pain, general health perceptions, physical role functioning, emotional role functioning, social role functioning, and mental health. Each scale is directly transformed into a 0 to 100 scale on the assumption that each question carries equal weight. Lower scores indicate more diminished health-related quality of life.

The SF-36 will only be completed for subjects when a validated version is available in the subject's native language.

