4.3 Exploratory Endpoints

The exploratory endpoints of the study include health related QoL, patient reported outcomes and biomarkers as listed below:

- Changes from baseline in 8 subscales and summary scores (PCS and MCS) in health-related quality of life as assessed by using Short Form Health Survey – 36 (SF-36v2);
- Changes from baseline in symptom severity score as measured by Patient Global Impression of Severity (PGI-S) and Patient Global Impression of Change (PGI-C) over the duration of the study;
- Changes from baseline in serum biomarkers: creatine kinase (CK), serum SA, and potential biomarkers of sialylation and other markers of muscle injury and remodeling;

- Changes in free serum SA levels to assess the drug concentration in the bloodstream resulting from treatment;
- Frequency and percentage of subjects with the presence of ManNac detected from urine testing.

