8.9.1 Short Form - 36 Health Survey

The Short Form -36 Health Survey (SF-36v2) version 2 is a validated 36-item questionnaire that yields an 8-domain scale scores and two component summary measures of health-related quality of life. It will be evaluated at Baseline, Week 12, Week 24, Week 36, and Week 48. The domain scales are as follows:

- Physical Functioning (PF): Items 3a, 3b, 3c, 3d, 3e, 3f, 3g, 3h, 3i, 3j .
- Role-Physical (RP): Items 4a, 4b, 4c, 4d.
- Bodily Pain (BP): Items 7, 8.
- General Health (GH): Items 1, 11a, 11b, 11c, 11d.
- Vitality (VT): Items 9a, 9e, 9g, 9i.
- Social Functioning (SF): Items 6, 10.
- Role-Emotional (RE): Items 5a, 5b, 5c.
- Mental Health (MH): Items 9b, 9c, 9d, 9f, 9h

The overall summary measures are as follows:

- Physical Health Component Score (PCS): domain scales PF, RP, BP, GH.
- Mental Health Component Score (MCS): domain scales VT, SF, RE, MH.

Descriptive summary statistics and GEE modeling will be presented for the eight scale scores and PCS and MCS component scores at each time point as well as the change from baseline.

8.9.2 Patient Global Impression of Severity (PGI-S) and Patient Global Impression of Change (PGI-C)

The PGI-S/PGI-C is a self-administered tool widely used in chronic pain clinical trials to indicate the patient's perception about the efficacy of treatment. The PGI-S is conducted at baseline and patient rates the severity of his/her condition on a 7-point categorical scale; the PGI-C is conducted at follow-up visits and a patient rate the change of his/her condition on a 7-point categorical scale. The scales are presented in the table below.

Summary statistics of baseline PGI-S will be reported. The number and percentage of subjects in each category of PGI-S will also be reported. For PGI-C, both summary statistics and GEE estimates will be presented for each time point.

PGI-S	PGI-C
1=Normal, not affected at all	-3=Very much worse
2=Borderline affected	-2=Much worse
3=Mildly affected	-1=Slightly worse
4=Moderately affected	0=No change
5=Markedly affected	+1=Slightly better
6=Severely affected	+2=Much better
7=Extremely affected	+3=Very much better

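### SAP 10.4 is headed SF-36 version 2, but its table fits only two-level role items and a six-level item 9; if the form used has more role levels, RP and RE leave the 0-100 scale

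*SAP*

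**What the plan says.** SAP 8.9.1 states "The Short Form -36 Health Survey (SF-36v2) version 2 is a validated 36-item questionnaire". SAP 4.3 and 8.9 also write SF-36v2, and the scoring appendix is headed "10.4 SF-36 v2® Scoring Algorithm". The protocol gives no version; its section 7.5.3.3 says only "The SF-36 will be completed by subjects at each visit beginning with the Baseline Visit".

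The table in SAP 10.4 implies a response format for each scale:

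- Role-Physical (RP): four items, raw score 4 to 8, range 4.
- Role-Emotional (RE): three items, raw score 3 to 6, range 3.
- Items 9a, 9d, 9e and 9h: reversed from six options, the third of which is "A Good Bit Of The Time".
- Vitality (VT): four item-9 questions, raw 4 to 24. Mental Health (MH): five item-9 questions, raw 5 to 30.

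The role items are not among the ten items that 10.4 recodes. On the target metric, SAP 10.1.2 says "Each scale is directly transformed into a 0 to 100 scale". The scale scores are then standardised with printed US means and SDs, weighted, and rescaled to PCS and MCS.

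SAP 8.9.1 plans descriptive summaries and GEE models for all eight scales and both components, and 10.6 also lists GEE for SF-36. SAP 4.3 and 10.6 class the endpoint as exploratory.

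**The concern.** A raw range in a scoring table fixes the number of levels per item. The RP and RE rows allow two levels, and the VT and MH rows need six. The SAP attaches the name version 2 to this table without showing that the version 2 form has those options. If the form offers more than two role levels, a fully complete questionnaire scored as printed gives RP and RE values above 100. Those values then pass through means, SDs and weights that were meant for a 0-100 scale. This is separate from the handling of skipped items.

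Change from baseline would not remove the problem. The transform divides by a range that is too small by a factor of k-1, so every RP and RE change is multiplied by k-1, and PCS and MCS inherit the excess. The SAP takes precedence over the protocol on analysis methods (SAP 1), so the printed table is what a programmer would implement.

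**Working it through.** **Inputs.** From SAP 10.4: the raw ranges above; the transform (raw - lowest) / range x 100; RP mean 81.19907, SD 33.79729, PCS weight 0.35119, MCS weight -0.12329; RE mean 81.29467, SD 33.02717, PCS weight -0.19206, MCS weight 0.43407; final step x 10 + 50.

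Assumed, because the documents do not give it: k levels per role item, coded 1 to k, with k the best answer.

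**The table as printed (k = 2).** RP runs from (4-4)/4 x 100 = 0 to (8-4)/4 x 100 = 100, and RE from (3-3)/3 x 100 = 0 to (6-3)/3 x 100 = 100. With every scale at its printed mean, PCS = MCS = 50.0. With every scale at 100, PCS = 57.87 and MCS = 62.14. The appendix is internally consistent for this format.

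**More role levels, printed ranges kept.** Maximum RP = (4k-4)/4 x 100 and maximum RE = (3k-3)/3 x 100. Both equal 100 x (k-1).

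| k | Max RP and RE | PCS / MCS with role scales at maximum, others at 100 |
|---|---|---|
| 2 | 100 | 57.87 / 62.14 |
| 3 | 200 | 62.45 / 71.63 |
| 4 | 300 | 67.02 / 81.13 |
| 5 | 400 | 71.60 / 90.62 |

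**One item moving one level.** Under the printed ranges a step is 100/4 = 25 points on RP and 100/3 = 33.3 on RE, whatever k is.

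- PCS per RP step: 25 / 33.79729 x 0.35119 x 10 = 2.60.
- MCS per RE step: 33.3 / 33.02717 x 0.43407 x 10 = 4.38.

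With ranges matched to k, each step is divided by k-1:

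| k | PCS per RP step, matched range | MCS per RE step, matched range |
|---|---|---|
| 3 | 2.60/2 = 1.30 | 4.38/2 = 2.19 |
| 4 | 2.60/3 = 0.87 | 4.38/3 = 1.46 |
| 5 | 2.60/4 = 0.65 | 4.38/4 = 1.10 |

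These comparisons change the raw range alone and keep the printed SDs and weights. Norms for another version are not in the documents.

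**Middle answer (3 of 5) on all seven role items.** RP = (12-4)/4 x 100 = 200 and RE = (9-3)/3 x 100 = 200. With matched ranges both are 50, for example (12-4)/16 x 100. The excess of 150 on each scale shifts:

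- PCS by 150/33.79729 x 3.5119 - 150/33.02717 x 1.9206 = 15.59 - 8.72 = +6.86.
- MCS by -150/33.79729 x 1.2329 + 150/33.02717 x 4.3407 = -5.47 + 19.71 = +14.24.

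With the other six scales at their printed means, PCS is 55.44 instead of 48.58 and MCS is 61.27 instead of 47.03. The scoring is linear, so the shift is the same whatever the other scales are.

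**Item 9, under a second assumption.** Suppose item 9 has five options stored as 1 to 5, and the reversed items go through the printed recode, which is 7 minus the code.

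- VT (two reversed, two not): best (6+6+5+5-4)/20 = 90%, worst (2+2+1+1-4)/20 = 10%.
- MH (two reversed, three not): best (27-5)/25 = 88%, worst (7-5)/25 = 8%.

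If the stored codes instead keep the printed label values and only code 3 is absent (1, 2, 4, 5, 6), both ends of VT and MH can be reached and this limit does not arise.

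**The case against.** The strongest objection is that the documents alone contain no contradiction. The 10.4 table agrees with itself, and neither document says how many response options the version 2 role items or item 9 have. A reader might infer that the SAP is shown to mis-score the SF-36, with role scores running to 400. The documents do not support that. They establish a named version and a table for one specific format; whether the two conflict depends on a form that is not printed. At k = 2 nothing is mis-scored.

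A reader might also infer that VT and MH cannot reach either end of their scale. That needs a further assumption about how item 9 is stored, and the SAP lists those recodes by response label.

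The objection on weight also stands. SF-36 is exploratory, and SAP 8.9 expects mostly descriptive analysis. The form is used only where a validated version exists in the subject's language, so fewer than the roughly 45 subjects may contribute. P-values are nominal, and efficacy is not powered.

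The objection does not remove the need to settle the version. SAP 10.1.2 defers to a published standard algorithm and cites sources dated 1995 and 2007, without saying which version each scores; neither is in the SAP reference list. From these documents a programmer cannot tell which of the label and the table to trust.

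**Conclusion.** The point holds as a conditional one. The documents show that 10.4 is labelled version 2 and that its arithmetic works only for two-level role items and a six-level item 9. On the assumption that the administered form has more than two role levels, following 10.4 breaks the SAP's own 0-100 scale. RP and RE can then reach 200, 300 or 400 for k = 3, 4 or 5, and at k = 5 a role item step counts four times its proper amount in PCS or MCS. The VT limits of 10-90 and MH limits of 8-88 hold only if item 9 also has five options stored as 1 to 5. If the form matches 10.4, the scores are sound and only the version label is wrong.

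The consequence is confined to an exploratory endpoint; the primary safety endpoint is untouched. It is still worth settling, because all ten SF-36 scores are committed to modelling and the check is nearly free.

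**What to change.** Before database lock, compare the response options on the CRF form with SAP 10.4.

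- **If they do not match:** replace the item 9 recodes, the RP, RE, VT and MH raw ranges, and the norm means, SDs and coefficients with the scoring for the version administered.
- **If they match:** keep the algorithm and correct the version label in 4.3, 8.9, 8.9.1 and the 10.4 heading.
- **In either case:** state the response options and stored codes in the SAP, and program a check that item codes lie in the expected range and every transformed scale lies within 0-100. The item-code check is needed because compressed VT or MH scores would pass a 0-100 check.

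The cost is a short SAP correction and, if the form does not match, reprogramming of the scoring. No new data are needed.
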